3.2 Primary Safety Endpoints

Safety will be described for all subjects:

1. Occurrence, nature (MedDRA systemic organ class [SOC] and preferred term [PT]), time to onset, number of days of occurrence, intensity, and relationship to investigational product of injection site reactions and systemic reactions occurring up to 7 days after administration of the investigational product
2. Occurrence, nature (MedDRA SOC and PT), time to onset, relationship to investigational product and outcome of SAEs throughout the study

3. Visual analogue scale (VAS) and (see comment) scores for injection site pain up to 7 days after administration of the investigational product
4. Occurrence of out-of-range from baseline biological test results up to 7 days post-last dose

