4 STUDY PLAN

4.1 Study Design

This will be a Phase 1, open label, single center, dose escalation study to evaluate the safety, tolerability, and pharmacokinetic profile of mAb AZD5396 and mAb AZD8076 following delivery of optimized dMAb AZD5396 and dMAb AZD8076 with different doses of Hylenex® Recombinant, administered by intramuscular injection (IM) followed immediately by electroporation (EP) using the CELLECTRA™ 2000 with side port needle device, in a five-dose (8 cohort) regimen in healthy adults.

Up to 50 healthy volunteers 18 to 60 years of age will be enrolled in this study and evaluated across eight cohorts (n=3 to 6 per cohorts A1, A2, B, C, and D; n=5 per cohorts E, F, and G). Participants will be administered dMAb AZD5396 and dMAb AZD8076 at a five-dose level of each plasmid:

- 0.5 mg single-dose (cohort A1),
- 1 mg single-dose (cohort A2),
- 1 mg two-dose (cohorts B and F),
- 2 mg two-dose (cohort C),
- 0.25 mg two-dose (cohort D),
- 4 mg two-dose (cohort E), and
- 2 mg four-dose (cohort G).

Participants will receive two injections (one per dMAb) into the arm (deltoid)/leg (quadriceps) region at Day 0 alone (groups A1 and A2) or on day 0 and 3 (groups B-F) or on days 0, 3, 28, 31 (cohort G). Injections may be given in different arms or in an arm (deltoid) and a leg (quadriceps). If preferred or needed both doses can be done in the deltoid region or the lateral quadriceps, although the injections should be in different areas separated by at least 2 cm. The Day 3 injections may repeat an area already used on Day 0 as long as separated by at least 2 cm. The Day 31 injections may repeat an area already used on Day 28 as long as separated by at least 2 cm. The Day 28 injections may repeat an area already used on Day 0 or Day 3 injections with no separation required given the time span between injections.

This study will adhere to a dose escalation scheme as described in [Figure 2](#).

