D	dMAb AZD5396 and dMAb AZD8076	Day 0, 3	6 (3+3)	2x (0.25 mg dMAb AZD5396) + 2x (0.25 mg dMAb AZD8076)	34U	0.25 mL	OpBlock 0078	0.5 mg dMAb AZD5396 + 0.5 mg dMAb AZD8076
E	dMAb AZD5396 and dMAb AZD8076	Day 0, 3	5	2x (2 mg dMAb AZD5396) + 2x (2 mg dMAb AZD8076)	75U (0.5 mL)	0.70 mL	OpBlock 0078	4 mg dMAb AZD5396 + 4 mg dMAb AZD8076
F	dMAb AZD5396 and dMAb AZD8076	Day 0, 3	5	2x (0.5 mg dMAb AZD5396) + 2x (0.5 mg dMAb AZD8076)	75U (0.5 mL)	0.55 mL	OpBlock 0070	1 mg dMAb AZD5396 + 1 mg dMAb AZD8076
G	dMAb AZD5396 and dMAb AZD8076	Day 0, 3, 28, 31	5	4x (0.5 mg dMAb AZD5396) + 4x (0.5 mg dMAb AZD8076)	75U (0.5 mL)	0.55 mL	OpBlock 0078	2 mg dMAb AZD5396 + 2 mg dMAb AZD8076
	TOTAL		44-50^d					

^a All subjects will receive the study product by IM route of administration. All doses of optimized dMAb AZD5396 and dMAb AZD8076 will be prepared with Hylenex® less than 4 hours before dosing of subjects. Doses of Hylenex will vary depending on the cohort to allow for a different volume per injection

^b Use of CELLECTRA™ 2000 with Side Port needle, OpBlock 0078 and 5P-IM Side Port Array or Profusion Therapeutic Infusion needle (G47574) for Cohorts A-E & G.

^c Use of CELLECTRA™ 2000 with Side Port needle, OpBlock 0070 and 5P-IM Side Port Array for Cohort F.

^d Note that the n is defined as evaluable participants. Due to partial doses or early dropouts, we may dose up to 50 participants total to reach enough evaluable participants in each cohort. See Protocol section [8.2](#) which describes replacing participants.

The decision to open new cohorts in the clinical trial is justified by several key factors. Firstly, ensuring safety is of utmost importance in any clinical trial. By introducing additional cohorts, we will gather more data on the safety profile of the investigational product.

Secondly, evaluating the levels of expression of dMAbs is crucial for assessing the efficacy of this approach. The expression levels directly impact the therapeutic potency and effectiveness *in vivo*. By expanding the cohorts, we will gather a larger sample size and thereby obtain more reliable data on the expression levels of dMAbs in different individuals. This broader understanding of expression levels will aid in determining optimal dosages and predicting the treatment's potential success.

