7.2 Dosing and Follow-Up Evaluations

Once eligibility has been confirmed, the participant will be assigned to receive Investigational product. Visit dates and windows must be calculated from Day 0.

7.3 Day 0, Day 3, Day 28, and Day 31

The following evaluations will be performed on Day 0 (all cohorts), Day 3 (cohorts B-G), Day 28 (cohort G), and Day 31 (cohort G) only prior to Investigational product administration:

- Collect all present and/or new or ongoing adverse events (including history of new COVID 19 diagnosis).
- Document any present conditions and concomitant illnesses.
- Record current concomitant medications/treatments.
- Targeted physical examination (driven by symptoms).
- Record vital signs pre injection including heart rate (HR), respiratory rate (RR), blood pressure (BP), oral temperature.
- Collect urine for urinalysis and urine pregnancy test (if WOCBP).
- Collect blood for PT(INR) and aPTT, CBC with differential, serum chemistry, CPK.
- Collect serum for mAb AZD5396 and mAb AZD8076 level assessment and ADA evaluation.
- Provide Memory Aid.

Investigational product administration should occur after all the above pre-dose procedures have been completed.

Participants will receive two injections into the arm (deltoid)/leg (quadriceps) region at day 0 (all groups), and on day 3. Injections will be separated by ~30 minutes. Injections may be given in different arms or in an arm (deltoid) and a leg (quadriceps). If preferred or needed both doses can be done in the deltoid region or the lateral quadriceps, although the injections should be in different areas separated by at least 2 cm. The Day 3 injections may repeat an area already used on Day 0 as long as separated by at least 2 cm. For Cohort G, the Day 28 injections may be repeated in an area already used, and the Day 31 injections may repeat an area already used on Day 28 as long as separated by at least 2 cm.

If a participant has a DLT, as outlined in the protocol, the second dose of the product will not be given.

The following evaluations will be performed on Day 0 (all cohorts), Day 3 (cohorts B-G), Day 28 (cohort G), and Day 31 (cohort G) after Investigational product administration:

- Conduct targeted injection site reaction systemic and local assessments 30 min post each injection.
- Record vital signs post each injection including heart rate (HR), respiratory rate (RR), blood pressure (BP), oral temperature. Participants will be observed for 1 hour after the last injection.

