7.5 Day 10 (cohorts B-G only)

The following evaluations will be performed at this visit:

- Conduct targeted injection site reaction systemic and local assessment.
- Collect all present and/or new or ongoing adverse events.
- Document any present conditions and concomitant illnesses (including history of new COVID 19 diagnosis).
- Record current concomitant medications/treatments.
- Targeted physical examination.
- Record vital signs including heart rate (HR), respiratory rate (RR), blood pressure (BP), oral temperature.
- Collect blood for PT(INR) and aPTT, CBC with differential, serum chemistry, CPK.
- Collect urine for urinalysis.

- Collect serum for mAb AZD5396 and mAb AZD8076 level assessment and ADA evaluation.
- Perform 12 lead ECG.

7.6 Week 2, Week 3, Week 4, Week 5, Week 6, Week 8, Week 12, Week 16, Week 24, and Week 52

The following evaluations will be performed at these visits:

- Conduct targeted injection site reaction systemic and local assessment (cohort G, Week 5 and 6).
- Collect all present and/or new or ongoing adverse events.
- Document any present conditions and concomitant illnesses (including history of new COVID 19 diagnosis).
- Record current concomitant medications/treatments.
- Targeted physical examination.
- Record vital signs including heart rate (HR), respiratory rate (RR), blood pressure (BP), oral temperature.
- Collect blood for PT(INR) and aPTT, CBC with differential, serum chemistry, CPK
- Collect urine for urinalysis.
- Collect serum for mAb AZD5396 and mAb AZD8076 level assessment and ADA evaluation.
- Perform 12-lead ECG

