9.5 Injection and Electroporation (EP)

Injections of investigational product are immediately followed by electroporation. Participants in Cohorts A1 and A2 will receive two injections of dMAb AZD5396 and dMAb AZD8076 in the deltoid/quadriceps followed immediately by EP on Day 0. Cohorts B-G will receive two injections of dMAb AZD5396 and dMAb AZD8076 in the deltoid/quadriceps followed immediately by EP on both Days 0 and 3, for a total of 4 injections. Cohort G will also receive two injections of dMAb AZD5396 and dMAb AZD8076 in the deltoid/quadriceps followed immediately by EP on Days 28 and 31, for a total of 8 injections. If preferred or needed, both doses can be done in the deltoid region or the lateral quadriceps on Days 0, 3, 28, and/or 31.

Study Agent must not be given within 2 cm of a tattoo, scar, or active lesion/rash. Also, IM injection followed immediately by EP must not be performed in the muscle of an extremity which has any metal hardware (e.g., surgical rods, pins or joint replacements). The two injections on Days 0, 3, 28, and/or 31 will be given on the same side deltoid and lateral quadriceps (i.e., left side or right side of the body). If preferred or needed, both doses can be done in the deltoid region or the lateral quadriceps.

The side-port needle should be inserted fully with firm pressure until injection is completed, then wait for a few seconds and then removed. Training on this method of injection will be provided.

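### Cohort G has no laboratory visit targeted at 7 days after its last dose, although a primary safety endpoint runs to that day and every other cohort has such a visit

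*Protocol*

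**What the plan says.** Section 3.2 of the protocol, repeated in the synopsis, defines the fourth primary safety endpoint as "Occurrence of out-of-range from baseline biological test results up to 7 days post-last dose". It fixes where the window ends, counted from the last dose.

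Table 2 and section 4.1 give the last dosing day as Day 0 for Cohorts A1/A2, Day 3 for B-F and Day 31 for G. Section 9.5 confirms that G is dosed again "on Days 28 and 31, for a total of 8 injections".

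Table 3 places safety laboratory tests at Day 7 ±1 for all of Cohorts A-F and at Day 10 ±1 for B-F. Table 4 gives Cohort G the same Day 7 and Day 10 visits, but these follow only its first pair of doses. After the Day 31 (±1) dose, G's next visits are Week 5 (±2 days) and Week 6 (±4 days). Section 7.6 requires at both: "Collect blood for PT(INR) and aPTT, CBC with differential, serum chemistry, CPK".

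Section 7.2 sets the anchor for all of these visits: "Visit dates and windows must be calculated from Day 0".

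**The concern.** The endpoint is counted from the last dose, but the visits are counted from Day 0. In Cohorts A-F the two agree at target. In Cohort G the endpoint closes on Day 38, and Table 4 has no visit targeted there.

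It looks like an oversight. Table 4 and section 7.6 add injection-site assessments for Cohort G at Weeks 5 and 6, the positions that Day 7 and Day 10 hold after the first pair of doses. Week 5 matches Day 7 exactly (4 days after the second dose of the pair). Week 6 misses the Day 10 equivalent by 4 days.

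At stake is a primary endpoint in the only cohort re-dosed about a month after its first doses, and the one with the most injections. The primary objective is to describe safety in each study group. A change in CPK, transaminases, coagulation or blood counts that first appears 5 to 7 days after the last dose would normally be sampled in time in B-F, but not in G when visits fall on target. No analysis plan can later supply a time point that was not sampled.

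**Working it through.** **Inputs.** Dosing days and windows: Table 2, Table 3 (Day 3 ±1) and Table 4 (Day 31 ±1). Laboratory visits: Table 3 (Day 7 ±1, Day 10 ±1) and Table 4 (Week 5 = Day 35 ±2, so Days 33-37; Week 6 = Day 42 ±4, so Days 38-46). Endpoint horizon: 7 days after the last dose (section 3.2).

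**Formulas.** Nominal lag = visit target − last-dose target. Shortest permitted lag = earliest visit day − latest dose day. Longest permitted lag = latest visit day − earliest dose day.

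**The protocol's 7 days, reproduced where it holds.**

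| Cohort | Visit | Nominal lag | Permitted lag |
|---|---|---|---|
| A1/A2 | Day 7 | 7 − 0 = 7 | 6 to 8 |
| B-F | Day 10 | 10 − 3 = 7 | 9 − 4 = 5 to 11 − 2 = 9 |
| G | Week 5 | 35 − 31 = 4 | 33 − 32 = 1 to 37 − 30 = 7 |
| G | Week 6 | 42 − 31 = 11 | 38 − 32 = 6 to 46 − 30 = 16 |

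A visit targeted at 7 days in Cohort G would fall on 31 + 7 = Day 38, which is only the first permitted day of the Week 6 window. With an on-time Day 31 dose, Week 5 lies 2 to 6 days and Week 6 lies 7 to 15 days after it, so 1 of the 9 permitted Week 6 days is inside the endpoint.

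**How often the windows rescue it.** Assume, for illustration only, that every permitted day is equally likely. Cohort G has 3 dose days × 5 Week 5 days × 9 Week 6 days = 135 combinations.

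- Week 6 falls within 7 days of the last dose in 15 of 135 (11%).
- The last in-window laboratory result is at 6 days or later in 22 + 19 = 41 of 135 (30%).
- For B-F (3 × 3 × 3 = 27 combinations of Day 3, Day 7 and Day 10) the matching figure is 8 + 9 = 17 of 27 (63%).

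**Dose and injection counts.** Total of each dMAb from Table 2: E, 2 × 2 mg = 4 mg; C, 2 × 1 mg = 2 mg; G, 4 × 0.5 mg = 2 mg; all others 1 mg or less. Injections: A1/A2 2, B-F 4, G 8.

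**Post-baseline laboratory draws inside the endpoint at target, counted from Day 0** (draws on dosing days are pre-dose, section 7.3): A1/A2, 1 (Day 7); B-F, 3 (Days 3, 7, 10); G, 8 (Days 3, 7, 10, Weeks 2 and 3, Days 28 and 31, Week 5).

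**The case against.** Several objections stand, and they limit what can be claimed.

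- **Direction of bias.** A reader might infer that Cohort G's laboratory safety will look better by construction. The documents do not support that. The endpoint fixes only the end of the window. Counted from Day 0, G has the longest window and 8 post-baseline draws inside it, against 3 in B-F and 1 in A1/A2. More draws mean more chances to record an abnormal value, so the opposite tendency is at least as plausible.
- **Heaviest dosing.** A reader might call G the most heavily dosed regimen. That is true of dosing days and injections only. Cohort E receives twice the total plasmid (4 mg against 2 mg of each dMAb).
- **A fixed cut to 4 days.** Four days is the value at target. The windows permit a last in-window result anywhere from 1 to 7 days after the last dose.
- **Lost data.** Full laboratory panels are drawn at Weeks 5, 6 and 8 and later. Section 11.3.1 summarises them by time point and cohort. Abnormalities that meet the AE criteria of section 10.1.1 are recorded and summarised through Week 72. A CPK rise still present at Week 6 would be seen and reported.
- **The comparators are not exact either.** In 3 of the 9 combinations of Day 3 and Day 10 dates, Day 10 falls 8 or 9 days after the last dose. A Day 8 visit in A1/A2 puts that cohort's only post-baseline draw outside a literal 7-day limit.

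It can also be said that the endpoint states an upper bound and does not require a sample on day 7. That is so, but every other cohort has a visit targeted at the bound and G does not.

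**Conclusion.** The point holds as a mismatch between a primary endpoint and the schedule of one cohort. At target dates, the last laboratory result inside the endpoint is at 4 days after the last dose in Cohort G and at 7 days in every other cohort. The next G result, at 11 days, is outside it. What is reduced is post-last-dose coverage and between-cohort comparability on this endpoint. Overall safety information is not lost, and no direction of bias is claimed.

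The conclusion rests on reading Weeks 5 and 6 as Days 35 and 42 from Day 0, as section 7.2 requires; section 9.9.1 itself equates Week 6 with Day 42. The 11%, 30% and 63% figures also rest on the equal-likelihood assumption; the nominal and permitted lags do not. Cohort G has 5 participants and the analysis is descriptive, so no power or error rate is affected. The change is worth making because it is cheap and the gap cannot be repaired at analysis.

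**What to change.** 1. **Table 4 and section 7.2.** For Cohort G only, time the Week 6 visit at 7 days (±1) after the actual Day 31 dose, mirroring Day 10 in B-F, and exempt it from the Day 0 anchor. An on-time dose puts it on Days 37-39. Over the permitted dose window (Days 30-32) it falls on Days 36-40, partly before the present Week 6 window, so the table must be amended.
2. **Keep Week 5 earlier.** Its present window runs to Day 37 and could coincide with the re-timed visit. Its Day 35 target always precedes the earliest re-timed date, Day 36; require that it take place on an earlier day than the re-timed visit.
3. **Section 3.2.** State that the scheduled 7-day visit (Day 7 for A1/A2, Day 10 for B-F, re-timed Week 6 for G) closes the endpoint even if, within its permitted window, it falls a day or two beyond 7 days. This also settles the late Day 7 and Day 10 visits in the other cohorts.
4. **Section 9.9.1.** Detection at the Day 42 (Week 6) visit triggers unscheduled PK sampling. State that for Cohort G the trigger applies to the re-timed visit.

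No visit is added and no dose or treatment rule changes. The cost is in PK/ADA timing. With an on-time dose, Cohort G's Week 6 sample is drawn 42 − 39 = 3 to 42 − 37 = 5 days before its target, and the gap to Week 8 (Day 56) widens from 14 days to 56 − 39 = 17 to 56 − 37 = 19 days.

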3.3 Primary Pharmacokinetic Endpoint

1. Detection of mAb AZD5396 and mAb AZD8076 serum following administration of dMAb AZD5396 and dMAb AZD8076 with Hylenex® delivered IM followed by EP with the CELLECTRA™ 2000 device.

3.4 Exploratory Objectives

1. To determine the Neutralizing SARS-COV-2 antibody titers of participants during the study.
2. To determine the antiviral activity of plasma of participants in the study when tested in an animal model of SARS-CoV-2 virus infection after the administration of dMAb AZD5396 and dMAb AZD8076.
3. To evaluate the incidence of new SARS-COV-2 infection for the duration of the study.

3.5 Exploratory Endpoint

1. Neutralizing antibody titer against SARS-COV-2 during the study
2. Frequency of SARS-COV-2 infection in animal models treated with passive transfer of serum from participants.
3. Frequency of new SARS-COV-2 infections for the duration of the study.

4 STUDY PLAN

4.1 Study Design

This will be a Phase 1, open label, single center, dose escalation study to evaluate the safety, tolerability, and pharmacokinetic profile of mAb AZD5396 and mAb AZD8076 following delivery of optimized dMAb AZD5396 and dMAb AZD8076 with different doses of Hylenex® Recombinant, administered by intramuscular injection (IM) followed immediately by electroporation (EP) using the CELLECTRA™ 2000 with side port needle device, in a five-dose (8 cohort) regimen in healthy adults.

Up to 50 healthy volunteers 18 to 60 years of age will be enrolled in this study and evaluated across eight cohorts (n=3 to 6 per cohorts A1, A2, B, C, and D; n=5 per cohorts E, F, and G). Participants will be administered dMAb AZD5396 and dMAb AZD8076 at a five-dose level of each plasmid:

- 0.5 mg single-dose (cohort A1),
- 1 mg single-dose (cohort A2),
- 1 mg two-dose (cohorts B and F),
- 2 mg two-dose (cohort C),
- 0.25 mg two-dose (cohort D),
- 4 mg two-dose (cohort E), and
- 2 mg four-dose (cohort G).

Participants will receive two injections (one per dMAb) into the arm (deltoid)/leg (quadriceps) region at Day 0 alone (groups A1 and A2) or on day 0 and 3 (groups B-F) or on days 0, 3, 28, 31 (cohort G). Injections may be given in different arms or in an arm (deltoid) and a leg (quadriceps). If preferred or needed both doses can be done in the deltoid region or the lateral quadriceps, although the injections should be in different areas separated by at least 2 cm. The Day 3 injections may repeat an area already used on Day 0 as long as separated by at least 2 cm. The Day 31 injections may repeat an area already used on Day 28 as long as separated by at least 2 cm. The Day 28 injections may repeat an area already used on Day 0 or Day 3 injections with no separation required given the time span between injections.

This study will adhere to a dose escalation scheme as described in [Figure 2](#).

Participants will be enrolled sequentially beginning with Cohort A1. The first participant in cohort A1 will be dosed 0.5 mg of each product once on Day 0 following confirmation of eligibility criteria. If no stopping event (DLT) is observed (see Section [10.10](#)) after 14 days of the initial dose, the remaining two participants in that cohort A1 will be dosed three days apart. If there are 0 DLT events after 14 days of the initial dosing of the third subject, cohort A2 will open and will follow the same schedule. Same process will be followed for the next cohorts with a total of 6 participants enrolled in each of cohort B to C (See [Figure 2](#)), 1 sentinel participant will be enrolled initially and, after 14 days of observation, the additional 5 participants will be enrolled three days apart each. If there are 0 DLT events past 14 days after the initial dosing of the last participant, the next cohort will open. Because cohorts D F, & G are a similar or lower dose and the safety profile have been already established in previous cohorts, the 14-day waiting periods will not apply to Cohorts D, F, or G. Even though the levels of expression observed in cohorts A-D are way below the levels seen when the monoclonal antibodies are given as protein, Cohort E will receive a higher dose which will require a 14 day waiting period after the dosing of the first participant at this level. Every participant in Cohort E following the 14 day waiting period will be dosed 3 days apart as done in other cohorts. Any DLT will be reported to the FDA in an expedited manner.

Table 2. Dosing Arms and Regimens

Cohort	Study Product	Dose Schedule	n	No. injections per dose (dose formulation in mg) 2 injections are given on each day	Hylenex dose per injection	Final volume per injection	EP parameters	Total dose of each dMAb (mg)
A1	dMAb AZD5396 and dMAb AZD8076	Day 0	3	1x (0.5 mg dMAb AZD5396) + 1x (0.5 mg dMAb AZD8076)	68U	0.5 mL	OpBlock 0078	0.5 mg dMAb AZD5396 + 0.5 mg dMAb AZD8076
A2	dMAb AZD5396 and dMAb AZD8076	Day 0	3	1x (1mg dMAb AZD5396) + 1x (1 mg dMAb AZD8076)	135U	1 mL	OpBlock 0078	1 mg dMAb AZD5396 + 1 mg dMAb AZD8076
B	dMAb AZD5396 and dMAb AZD8076	Day 0, 3	6 (3+3)	2x (0.5 mg dMAb AZD5396) + 2x (0.5 mg dMAb AZD8076)	66.5U	0.5 mL	OpBlock 0078	1 mg dMAb AZD5396 + 1 mg dMAb AZD8076
C	dMAb AZD5396 and dMAb AZD8076	Day 0, 3	6 (3+3)	2x (1 mg dMAb AZD5396) + 2x (1 mg dMAb AZD8076)	135U	1 mL	OpBlock 0078	2 mg dMAb AZD5396 + 2 mg dMAb AZD8076
D	dMAb AZD5396 and dMAb AZD8076	Day 0, 3	6 (3+3)	2x (0.25 mg dMAb AZD5396) + 2x (0.25 mg dMAb AZD8076)	34U	0.25 mL	OpBlock 0078	0.5 mg dMAb AZD5396 + 0.5 mg dMAb AZD8076
E	dMAb AZD5396 and dMAb AZD8076	Day 0, 3	5	2x (2 mg dMAb AZD5396) + 2x (2 mg dMAb AZD8076)	75U (0.5 mL)	0.70 mL	OpBlock 0078	4 mg dMAb AZD5396 + 4 mg dMAb AZD8076
F	dMAb AZD5396 and dMAb AZD8076	Day 0, 3	5	2x (0.5 mg dMAb AZD5396) + 2x (0.5 mg dMAb AZD8076)	75U (0.5 mL)	0.55 mL	OpBlock 0070	1 mg dMAb AZD5396 + 1 mg dMAb AZD8076
G	dMAb AZD5396 and dMAb AZD8076	Day 0, 3, 28, 31	5	4x (0.5 mg dMAb AZD5396) + 4x (0.5 mg dMAb AZD8076)	75U (0.5 mL)	0.55 mL	OpBlock 0078	2 mg dMAb AZD5396 + 2 mg dMAb AZD8076
	TOTAL		44-50^d					

^a All subjects will receive the study product by IM route of administration. All doses of optimized dMAb AZD5396 and dMAb AZD8076 will be prepared with Hylenex® less than 4 hours before dosing of subjects. Doses of Hylenex will vary depending on the cohort to allow for a different volume per injection

^b Use of CELLECTRA™ 2000 with Side Port needle, OpBlock 0078 and 5P-IM Side Port Array or Profusion Therapeutic Infusion needle (G47574) for Cohorts A-E & G.

^c Use of CELLECTRA™ 2000 with Side Port needle, OpBlock 0070 and 5P-IM Side Port Array for Cohort F.

^d Note that the n is defined as evaluable participants. Due to partial doses or early dropouts, we may dose up to 50 participants total to reach enough evaluable participants in each cohort. See Protocol section [8.2](#) which describes replacing participants.

The decision to open new cohorts in the clinical trial is justified by several key factors. Firstly, ensuring safety is of utmost importance in any clinical trial. By introducing additional cohorts, we will gather more data on the safety profile of the investigational product.

Secondly, evaluating the levels of expression of dMAbs is crucial for assessing the efficacy of this approach. The expression levels directly impact the therapeutic potency and effectiveness *in vivo*. By expanding the cohorts, we will gather a larger sample size and thereby obtain more reliable data on the expression levels of dMAbs in different individuals. This broader understanding of expression levels will aid in determining optimal dosages and predicting the treatment's potential success.

Lastly, exploring different approaches to enhance the expression levels of dMAbs *in vivo* is a logical step forward. By opening new cohorts, we will introduce and test various strategies aimed at increasing the expression levels. These approaches may include novel delivery methods that will evaluate the tolerability of electroporation using alternative parameters and modified formulations. This exploration of different avenues increases the chances of finding innovative solutions to optimize the expression levels of dMAbs, potentially enhancing the treatment's efficacy and therapeutic impact.

In conclusion, opening new cohorts in the clinical trial is justified by the need to ensure safety, assess the expression levels of dMAbs, and explore diverse strategies to increase expression levels *in vivo*. This multifaceted approach strengthens the research process and provides a more comprehensive understanding of the investigational treatment, ultimately paving the way for improved therapeutic outcomes. The rationale for redosing participants with a DNA-encoded monoclonal antibody (dMAb) after 52 weeks is to evaluate the long-term efficacy and potential for sustained antibody presence in the system. This interval is strategically chosen based on the expected duration of dMAb-induced antibody production, hypothesizing that a yearly boost could reinforce the therapeutic effects.

[figure not shown]
